VMN's are more efficient and deliver higher concentrations of medication in simulated lung models when compared to JN's.[7-10] In a recent simulated lung model study the combination of a VMN and VM delivered significantly more medication than a JN with AM, and when VMN was used with a mouthpiece there was almost an 8 fold increase in drug delivery.[7] Further studies are needed to assess the clinical efficacy of delivering higher dosages.

3. Concise Summary of Project:

This study will compare clinical outcomes of using a JN with AM or MP versus VMN with VM or MP in the treatment of acute moderate to severe asthma in CMCED. Patients will be treated according to CMCED's current Acute Asthma Clinical Pathway Algorithm for ED (AACPA) and randomized to receive aerosol therapy via JN with AM or MP (control group) or VMN with VM or MP (study group). Study personnel will screen CMCED census through the EMR for patients diagnosed with acute asthma exacerbation with an initial assessment of moderate to severe asthma (AS 5-12), according to the AACPA. Study personnel will approach the parents for study consent as soon as possible after CMCED admission and before any bronchodilator treatment begins. We are evaluating nebulizer devices in this study. Investigators and treating physicians will be blinded to which nebulizer was assigned to each patient. Primary study outcomes will be hospital admission rates. Secondary study outcomes will be number of treatments and length of stay in CMCED.

4. Study Procedures:

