Upon admission to CMCED patients diagnosed with acute asthma exacerbation will receive an initial assessment and asthma score (AS), per the AACPA. Patients assessed with moderate to severe asthma exacerbation (Moderate; AS 5-8, Severe; 9-12) will be eligible for enrollment in the study. Patients with impending respiratory failure will not be approached for enrollment. Once enrolled, patients will be randomized to receive aerosol therapy via JN with AM or MP (control group) or VMN with VM or MP (study group). Randomization process will consist of numbering 220 envelopes from 1-220 (110 for each arm). Using a simple randomization method each numbered envelope will be assigned to study or control group with a corresponding card placed inside indicating JN or VMN. Envelopes will then be sealed and held by PI. Envelopes will be assigned to study subjects in numerical order. Mask or mouthpiece selection will be made based on patient's age and/or ability to comply with using a mouthpiece. Patients will be treated according to CMCED's AACPA with the following modifications to allow for blinding and data collection:

Phase 1a (1st hour)

- According to AACPA initial treatment consists of three β-agonist treatments (albuterol & Ipratropium), which can be delivered in 20-minute increments or combined and given continuously over one hour. For blinding and assessment purposes 3 intermittent treatments will be given instead of continuously for this study.
- Two study personnel will be used to provide treatment:
 - One will administer all treatments with assigned nebulizer, perform pre-study assessments and note the start time of the treatment. Once aerosol treatments are completed the assigned nebulizer will be placed in a non-transparent bag for blinding.
 - The second "blinded" study personnel will perform post assessment and assign an AS.
- Since JN and VMN aerosolization rates differ, post assessment by blinded study personnel will not occur until 20 minutes has elapsed from initiation of treatments.
- Patients will receive an AS after each treatment and will be treated accordingly.
- If after the 1st treatment a patient receives an AS of 1-4 (mild) they will be treated according to the "mild" pathway.
- If patients receive an AS of 5-12 (moderate to severe) they will receive their 2nd treatment and/or 3rd treatments.
- Patients will continue to be assessed and scored every 20 minutes regardless of AS.

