- This procedure will be repeated until all 3 three treatments and/or assessments are completed in Phase 1a of AACPA.

- Once patients have finished treatments in Phase 1a they will either move to Phase 1b, be discharged or be admitted per AACPA guidelines.
- For consistency in CMCED length of stay and discharge criteria patients will be monitored for 40 minutes after their last treatment before discharge orders.
- If at any time or any Phase, the patient is deemed to be in impending respiratory failure by treating physician, they will be removed from the study and be treated according to physician orders.

Phase 1b (2nd hour)

- Treatments will be administered in the same fashion as Phase 1a with their assigned nebulizer.
- If an additional hour long treatment is ordered per AACPA, 3 intermittent treatments given in 20 minute increments will be administered in the same manner as Phase 1a.
- Once patients have finished treatments in Phase 1b they will either move to Phase 1c, be discharged or admitted per AACPA guidelines.

Phase 1c (3rd hour)

- If patients advance to Phase 1c, they will receive subsequent aerosol treatments and assessments in the same manner until they are either (1) admitted to hospital, or (2) discharged from CMCED per AACPA guidelines/pathway.
- If continuous bronchodilator treatment is ordered per AACPA in Phase 1c then study procedure will stop and patient will be treated per standard practice using large volume jet nebulizer.

5. Sub-Study Procedures:

N/A

6. Criteria for Inclusion of Subjects:

2 to 18 year old (up to 19th birthday) otherwise healthy children with primary diagnosis of acute moderate to severe exacerbation of asthma presenting to Children's Medical Center Emergency Department, Dallas.

7. Criteria for Exclusion of Subjects:

- Children < 2 years old
- Children with comorbid/complex medical conditions such as: congenital or acquired cardiovascular disease, cystic fibrosis, chronic lung disease (other than asthma), bronchopulmonary dysplasia, airway anomalies (e.g., tracheomalacia) or immunodeficiency syndromes.
- Patients with coexisting medical condition such as pneumonia
- Patients in impending respiratory failure as determined by treating physician
- Patients that have had oral corticosteroids within 24hrs of CMCED admission
- Patients that have had bronchodilator treatment within one hour of CMCED admission

8. Sources of Research Material:

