Patient's well-being and medical status will be monitored by CMCED staff throughout their emergency department stay in line with current standards of care and according to the AACPA. Vital signs will be monitored pre and post each aerosol treatment. If a vital sign is noted to be abnormal or an adverse event occurs, the RT or nurse for that patient will notify treating physician and PI. There will be a written report created of any adverse events that occur during treatments and a report will be made to the PI and the PI's faculty sponsor within 24 hours. Any reported adverse events will be reviewed at the time they are reported to determine if the adverse event was in any way caused by the study procedure. Any events deemed due to the study procedure will cause the study to be halted and further reviewed. Changes to the study procedure will be made as needed and reported to the IRB. The study will resume upon approval. Data will also be reviewed weekly by PI and co-investigator for any trends in safety concerns.

12. Procedures to Maintain Confidentiality:

To protect subject confidentiality, all data will be kept in a password-protected Excel database and all hard copies of data case report forms will be stored in a locked filing cabinet within PI's badge access restricted office. Only PI will have key to locked cabinet. Subjects will be given a study identification number, and patient identifiers will not be included in the database or hard copies of files. No patient name or identifying information will be included in any dissemination of study findings. The master list that links patient identifiers to the study subject will be kept recorded in a secure password protected EXCEL spreadsheet and paper copy under lock at the Pls office. It will be made very clear during the consent procedure that the patient/legal guardian will be free to withdraw from the study at absolutely any time, for any reason. Upon completion of data collection, all PHI will be de-identified. Only the study team will have access to study records and data. If a patient revokes authorization for participation in the study, all data will be discarded and will not be used. Data will be collected during the study days, specifically for purpose of the study

13. Potential Benefits:

Potential benefits derived from use of VMN for research subjects are:

- Decreased treatment times
- Fewer overall treatments
- Decreased time in Emergency Department
- Decreased admissions

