- Decreased medication dosages

Potential benefits derived from use of VMN to others with similar problems are:

- Decreased treatment times
- Fewer overall treatments
- Decreased Emergency Department and/or primary care physician visits
- Decreased hospital admissions
- Decreased medication dosages
- Better control of symptoms and/or exacerbations

Potential benefits to society derived from use of VMN are:

- Decreased healthcare costs
- Decreased Emergency Department utilization

14. Biostatistics:

Original Power/Sample Size Calculation

Based on a comparable study[11], the hospital admission rate is estimated to be 60% in the jet nebulizer group and 33% in the vibrating mesh nebulizer group, respectively. A sample size of 60 patients per group (120 patients in total) will achieve 80% power to detect statistically significant difference in hospital admission rates between the two groups (significance level=0.05, 2-sided).

Blinded Interim Power Analysis

At 108 patients a blinded interim power analysis revealed the rate of hospitalization is 20/108 or 18.5%. This is considerably lower than the rates anticipated in the original design. This is an indication that either the study population is much different than the population in the referenced work or the implementation of the intervention is different in this study. The overall rate of admission was around 45% in the referenced work. As an estimate of the effect of the intervention, maintaining something similar to a 2 to 1 admission rate between arms, this would indicate the comparison will be between one arm with a 12.5% admission rate and a second arm with a 27.5% admission rate. The same power calculation as before is repeated here for the lower rates which are more in line with what is being observed. This indicates that the shift in rates does have an impact on the power of the study. The study would require 220 subjects to still have 80% power to detect the difference. At the current sample size of 120, the study only has 53.8% power.

1. Shrestha, M., et al., *Continuous vs intermittent albuterol, at high and low doses, in the treatment of severe acute asthma in adults*. Chest, 1996. **110**(1): p. 42-7.

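### The protocol removes randomised children in impending respiratory failure from the study and does not say that their hospital admission still counts in the primary comparison

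*Combined protocol and SAP*

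**What the plan says.** The primary outcome is in Section 3: "Primary study outcomes will be hospital admission rates". The same section states that "Investigators and treating physicians will be blinded to which nebulizer was assigned to each patient".

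Section 4 keeps children who are already in this state out of the trial: "Patients with impending respiratory failure will not be approached for enrollment". Section 7 lists the same condition as an exclusion. A further bullet, placed under Phase 1a but worded to cover every phase, deals with a child who reaches this state later. A child "deemed to be in impending respiratory failure by treating physician, they will be removed from the study and be treated according to physician orders".

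Phase 1c handles a different event, an order for continuous bronchodilator treatment, in different words: "then study procedure will stop and patient will be treated per standard practice using large volume jet nebulizer". That child is not said to leave the study.

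Only one rule says what happens to the data of a child who leaves. It is in Section 12 and concerns withdrawal of permission: "If a patient revokes authorization for participation in the study, all data will be discarded and will not be used".

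Section 14 contains the two sample size calculations and nothing else. It gives no analysis population, no intention-to-treat statement and no rule for missing or replaced patients.

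**The concern.** Children in impending respiratory failure at entry are never enrolled, so the removal rule can only act on children who have been enrolled. It operates after randomisation, while the assigned device is in use. The trigger is clinical deterioration, which is closely tied to admission and which the device may itself affect.

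If removed children are left out of the analysis, the groups compared are no longer the groups randomised, and the losses are mostly primary events. Blinding of the treating physician limits selective removal. It does not prevent a real difference between devices in how many children deteriorate.

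The contrast with Phase 1c makes the literal reading plausible: there only the study procedure stops, whereas here the child is removed from the study. Two analysts working from this text could build different primary datasets, and the choice might be made after results by arm are known.

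**Working it through.** **Inputs from the document.** Section 14 plans for "one arm with a 12.5% admission rate and a second arm with a 27.5% admission rate", with 220 patients for 80% power, and states 53.8% power at 120. The test level is 0.05, two-sided. Section 4 gives 110 per arm. Section 14 does not say which arm has which rate; I take 27.5% as JN and 12.5% as VMN, following the study hypothesis.

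**Assumptions.** The share removed in each arm, r, is not in the document. Nor is the share c of removed children who would be admitted; I use c = 1 unless stated.

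**Formulas.** With true admission rate a, the rate seen after removal is p = (a − c·r)/(1 − r), on n = 110(1 − r) children. Power is Φ[(Δ − 1.96·SE0)/SE1], where Δ is the difference in p, SE0 = √[p̄(1 − p̄)(1/n1 + 1/n2)] and SE1 = √[p1(1 − p1)/n1 + p2(1 − p2)/n2].

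**The plan's own figures.**
- 60 per arm: SE0 = 0.0730, SE1 = 0.0717; (0.15 − 1.96 × 0.0730)/0.0717 = 0.096; power 53.8%, as stated.
- 110 per arm: SE0 = 0.0539, SE1 = 0.0530; (0.15 − 1.96 × 0.0539)/0.0530 = 0.84; power 79.8%, against 80% stated.

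Both reproduce. Neither calculation allows for removals.

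**One case in full: 5% of JN and 2% of VMN removed.**
- JN: (0.275 − 0.05)/0.95 = 23.7% of 104.5.
- VMN: (0.125 − 0.02)/0.98 = 10.7% of 107.8.
- Difference 13.0 points; SE0 = 0.0517, SE1 = 0.0512; power 71%.

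**Range of cases.**

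| Removed, JN / VMN | Admission seen | Difference (points) | Risk ratio | Power |
|---|---|---|---|---|
| none | 27.5% / 12.5% | 15.0 | 0.455 | 79.8% |
| 1 child / 1 child | 26.8% / 11.7% | 15.1 | 0.436 | 81% |
| 2 children / 1 child | 26.2% / 11.7% | 14.5 | 0.447 | 78% |
| 1% / 0.5% | 26.8% / 12.1% | 14.7 | 0.451 | 79% |
| 5% / 2% | 23.7% / 10.7% | 13.0 | 0.452 | 71% |
| 1% / 2% | 26.8% / 10.7% | 16.1 | 0.400 | 86% |

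The 86% is not a gain; it reflects an exaggerated difference. In the 5%/2% case, power is 74% if c = 0.8 and 78% if c = 0.5, and the risk ratio hardly moves. How serious the distortion looks therefore depends on the effect scale.

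**No true difference (20% admission in both arms).** Equal removal leaves equal rates and no bias. Removal of 1%/2% falsely favours VMN 3.6% of the time, against a nominal 2.5%; 2%/1% falsely favours JN equally often.

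**The interim count.** Section 14 reports: "At 108 patients a blinded interim power analysis revealed the rate of hospitalization is 20/108 or 18.5"%. It does not say whether removed children are in that count. If two admitted children were left out of both numbers, the pooled rate would be (20 + 2)/(108 + 2) = 20.0%; if four, (20 + 4)/(108 + 4) = 21.4%. The resizing used 12.5% and 27.5%, which average (12.5 + 27.5)/2 = 20.0%. Holding their ratio, power at 110 per arm is 79.8% at a pooled 20.0% and 83.2% at 21.4% (29.5% versus 13.4%).

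**The case against.** The strongest reply is that the phrase only releases the child from protocol treatment. It stands in a list of emergency department procedures and goes straight on to treatment under physician orders. Where the authors meant data to be dropped, in Section 12, they said so plainly, and only for revoked authorization. This has force: a reader might infer that the protocol plans to exclude these children from the analysis, and the document does not establish that. But the different Phase 1c wording points the other way, and no sentence settles it. The ambiguity stands.

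The second reply concerns frequency. Children in this state at entry, and those with complex conditions, are not enrolled, and the physician who makes the call is stated to be blinded. Removals may be very few, and every rate above is assumed. That also stands. Larger effects can be produced: 8% of JN and 2% of VMN removed would give 10.5 points and 55% power. But that discards 8.8 of 30.25 expected JN admissions, about 29%. It is an extreme case with no support in the document, and the point does not rest on it.

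A reader might also infer that uncounted removals undermine the sample size revision. They do not. The planning rates already average 20.0%, above the observed 18.5%, so two to four more admissions would leave power unchanged or slightly higher.

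Finally, the root gap is wider, since Section 14 names no analysis population at all. That is true, but this rule is where the gap touches the primary outcome directly, because the text itself takes children out after randomisation.

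**Conclusion.** The point holds as an unresolved rule about who is counted for the primary outcome; it does not show that bias has occurred. Taken literally, the protocol drops randomised children for a reason closely tied to admission, and nothing elsewhere restores them.

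The size runs from negligible to material and cannot be narrowed from the document. With a removal or two, power moves by a couple of percentage points in the likelier direction (more JN than VMN removals, if VMN works). At 5%/2%, with all removed children admitted, about 2 points of the difference and 9 points of power are lost. At 1%/2% the difference is overstated by about 1 point. The direction depends on which arm loses more children. If removals are rare the effect is small, and equal removal creates no difference where none exists.

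It should be fixed because the remedy is cheap and takes the choice out of the analyst's hands. Confidence is medium, limited by the unknown removal rate and the open reading of the phrase.

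**What to change.** Leave the clinical rule as it is and settle only the status of these children in the analysis:

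- In Section 4, state that removal for impending respiratory failure ends study procedures only, and that the child remains in the trial for outcome recording.
- In Section 14, state that hospital admission is recorded for every randomised child and analysed in the assigned arm, including children whose study procedure stops in Phase 1c. The only exception is revoked authorization, which stays as Section 12 has it.
- Report the number of removals by arm, and note whether any removed child is in the 20/108 count. The note is for clarity and does not reopen the sample size.

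The cost is a few sentences and a record look-up for any child already removed among the 108 or more enrolled. No extra patients are needed.

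### Section 14 presents 12.5% vs 27.5% as following from 18.5% overall and roughly 2:1, but these rates average 20.0% with a ratio of 2.2, so the 80% power rests on an unlabelled planning assumption

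*Combined protocol and SAP*

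**What the plan says.** All of this is in the combined protocol and SAP.

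- **Section 14, Original Power/Sample Size Calculation.** The first design assumed that "the hospital admission rate is estimated to be 60% in the jet nebulizer group and 33% in the vibrating mesh nebulizer group", with 60 patients per group, 80% power and a two-sided 0.05 level.
- **Section 14, Blinded Interim Power Analysis.** At 108 patients "a blinded interim power analysis revealed the rate of hospitalization is 20/108 or 18.5" per cent. The effect is carried over by "maintaining something similar to a 2 to 1 admission rate between arms", and the text concludes that "this would indicate the comparison will be between one arm with a 12.5% admission rate and a second arm with a 27.5% admission rate". These are described as "the lower rates which are more in line with what is being observed". Two results follow: "The study would require 220 subjects to still have 80% power to detect the difference", and "At the current sample size of 120, the study only has 53.8% power". The calculation is said to be the same one as before.
- **Section 4, Study Procedures.** Allocation is equal: "Randomization process will consist of numbering 220 envelopes from 1-220 (110 for each arm").

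**The concern.** The paragraph gives two inputs, an observed overall rate and an approximate ratio, and presents the two arm rates as their consequence. With equal allocation, an overall rate and a ratio fix both arm rates, so the step can be checked. The stated pair does not come out of it: the average is 20.0% rather than 18.5%, and the ratio is 2.2 rather than 2.0. A higher overall rate at a given ratio, and a larger ratio at a given overall rate, both raise power, so both departures favour the stated figure.

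The 80% figure is the stated justification for going from 120 to 220 children on the primary outcome. If the trial ends without a significant difference, readers will use Section 14 to judge how informative it was. They should be able to see that 80% belongs to an assumed 20% overall rate and was not read off the blinded data.

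**Working it through.** **Inputs.** Overall rate m = 20/108 = 0.1852; ratio about 2; arm rates 0.125 and 0.275; totals of 120 and 220 (all Section 14). Equal arms, 110 each (Section 4). Two-sided 0.05, stated for the original calculation and carried over because the text says the method is unchanged. No dropout allowance is stated, so none is applied.

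**Step 1. Do the rates match the inputs?**

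- Average: (12.5 + 27.5)/2 = 20.0%, against 18.5% observed.
- Ratio: 27.5/12.5 = 2.2, against roughly 2.
- With equal arms, low rate = 2m/(1 + r) and high rate = r × low rate. At m = 0.1852, r = 2.0 gives 12.3% vs 24.7%, and r = 2.2 gives 11.6% vs 25.5%. Neither is the stated pair.

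**Step 2. Reproduce the plan's power.** Two-proportion z-test with pooled null variance and no continuity correction, n per arm:

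- s0 = √[2p̄(1 − p̄)/n], where p̄ is the mean of the two rates
- s1 = √[(p1(1 − p1) + p2(1 − p2))/n]
- power = Φ[(|p1 − p2| − 1.96·s0)/s1]

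For 12.5% vs 27.5%:

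- n = 110: s0 = 0.0539, s1 = 0.0530; Φ(0.836) = 79.8%
- n = 60: s0 = 0.0730, s1 = 0.0717; Φ(0.096) = 53.8%

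Both stated figures are reproduced. The matching sample-size formula gives 111 per arm (222), in effect the stated 220.

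**Step 3. Same formula at 18.5% overall, 110 per arm** (s0 = 0.0524 throughout):

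| Held fixed | Arm rates | s1 | Power at 220 | Total for 80% |
|---|---|---|---|---|
| Ratio 2.0 | 12.3% vs 24.7% | 0.0517 | Φ(0.402) = 65.6% | 310 |
| Ratio 2.2 | 11.6% vs 25.5% | 0.0515 | Φ(0.703) = 75.9% | 244 |
| Difference of 15 points | 11.0% vs 26.0% | 0.0514 | Φ(0.921) = 82.2% | 210 |

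Two further cases, from the original design's rates: the rate ratio 60/33 = 1.82 gives 53.7%, and the odds ratio (0.60/0.40)/(0.33/0.67) = 3.05 gives 86.4%.

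**Step 4. How firm is 18.5%?** The 95% Wilson interval for 20/108 is 12.3% to 26.9%. At a true rate of 20%, 108 × 0.20 = 21.6 admissions are expected, and the probability of 20 or fewer is 0.40. At ratio 2.2, power with 220 patients runs from 55% to 93% across that interval.

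**Step 5. How far does the formula carry?** It reproduces the re-estimation but not the original calculation. For 60% vs 33% at 60 per arm it gives 85.2%, and it needs only 53 per arm for 80%. With a continuity correction the original design does come out at 60 per arm, but the re-estimation would then be 124 per arm (248). The absolute figures in step 3 therefore belong to the uncorrected formula. The drop between the stated rates and 18.5% at ratio 2.2 is similar under other methods: 80.4% to 76.7% for the exact power of the chi-square test, and 74.7% to 70.1% with the continuity correction.

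**The case against.** The strongest reply is that the paragraph is openly approximate. The ratio is hedged, the new rates are only said to be closer to what was observed, and nowhere does the text claim that they average 18.5%. The gap between 20.0% and 18.5% is less than two admissions in 108. At ratio 2.2, 22 admissions instead of 20 would give 80.8% power at 220. This stands as a limit on weight: 12.5% and 27.5% are admissible planning rates. It does not remove the point, because the text presents the pair as indicated by the stated inputs and never says that the planning average was set at 20%.

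A reader might infer that the power calculation is wrong and that the true power is 76%, not 80%. The documents do not support that. The power is correct for the rates stated. The ratio of 2.2 is only implied by the chosen pair, and the answer at 18.5% depends on what is held fixed: two of the cases above exceed 80%. For the same reason 244 is not a corrected sample size.

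Unequal arms at the interim would not explain the gap readily. For 12.5% and 27.5% to average 18.5%, about 65 of the 108 patients would have to be in the low-rate arm and 43 in the other. The documents report no such split, and the 220 calculation uses equal arms.

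The 15-point case giving 82% is a fair alternative, although Section 14 describes the effect it carries over as a ratio and not as a difference.

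**Conclusion.** The concern holds as a fault in the derivation, not in the power arithmetic. The rates of 12.5% and 27.5% do not follow from 18.5% overall and roughly 2:1. They average 20.0% with a ratio of 2.2, and Section 14 does not say that they are assumptions. For those rates the stated 80% at 220 and 53.8% at 120 are right. At the observed overall rate, power at 220 is about 66% for exactly 2:1, about 76% for 2.2 and about 82% for a fixed 15-point difference. The 76% is one scenario, about 4 points below the stated figure.

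This rests on equal arms, a two-sided 0.05 level, no dropout allowance, and the uncorrected pooled z-test, which matches the re-estimation but not the original 60 per arm. Severity is minor: the discrepancy is well within the sampling error of 20/108 and changes neither conduct nor analysis.

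**What to change.** Keep 220 and restate the paragraph in Section 14 along these lines:

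> The rates of 12.5% and 27.5% (20% overall, rate ratio 2.2) are planning assumptions compatible with, but not derived from, the blinded rate of 20/108. For these, 220 patients (110 per arm) give 80% power and 120 give 53.8%. At 18.5% overall, 220 patients give about 66% power for a ratio of 2.0, about 76% for 2.2, and about 82% for a 15-point difference.

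Give no reason for choosing these rates unless the sponsor can document one. The original design's rate ratio (about 54%) and odds ratio (about 86%) may be added as labelled sensitivity cases.

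The cost is rewording only, with no extra patients. The downside is that the stated power becomes less favourable under the ratio the protocol names.

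### No described analysis of hospital admission uses the baseline asthma score; pre-specified adjustment would recover some precision at 220 patients, by a modest and assumption-dependent amount, at almost no cost

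*Combined protocol and SAP*

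**What the plan says.** Section 3 makes hospital admission the primary outcome. Section 14 (Biostatistics) then gives two power calculations and stops. The first says "A sample size of 60 patients per group (120 patients in total) will achieve 80% power" at admission rates of 60% and 33%, two-sided 0.05. The second follows the blinded look: "At 108 patients a blinded interim power analysis revealed the rate of hospitalization is 20/108 or 18.5" per cent. It assumes 27.5% against 12.5%, says "The same power calculation as before is repeated here for the lower rates", reports 53.8% power at 120 patients, and concludes "The study would require 220 subjects to still have 80% power to detect the difference". No test, model, covariate or effect measure is named for the final analysis.

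Section 4 says "Upon admission to CMCED patients diagnosed with acute asthma exacerbation will receive an initial assessment and asthma score (AS), per the AACPA"; only patients scoring 5 to 12 are eligible. Section 8 lists asthma scores among the data taken from the medical record. On allocation, Section 4 says "Using a simple randomization method each numbered envelope will be assigned to study or control group"; no strata are mentioned.

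**The concern.** The enlargement to 220 brings power back only to about 80%, so there is no slack. A severity score is already held for every patient before allocation, and the treatment pathway acts on it. If it predicts admission, adjusting for it removes outcome variation unrelated to the nebulizer and sharpens the comparison without another patient. The plan does not use it in the analysis or in the allocation.

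Adjustment is best fixed in advance. A covariate or test chosen after outcomes by arm are known invites the suspicion that the result drove the choice. At stake is a modest amount of precision, together with a clear record of what the primary analysis is.

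**Working it through.** **1. Reproduce the plan's figures.** Inputs (Section 14): p1 = 0.275, p2 = 0.125, two-sided 0.05. Section 4 gives 110 envelopes per arm. For the pooled, uncorrected comparison of two proportions with n per arm and mean rate p = (p1 + p2)/2,

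power = Φ{ [ |p1 − p2|√n − 1.960 √(2p(1 − p)) ] / √( p1(1 − p1) + p2(1 − p2) ) }.

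Here p = 0.20, √(2 × 0.20 × 0.80) = 0.5657 and √(0.1994 + 0.1094) = 0.5557.

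- n = 110: (1.5732 − 1.1087)/0.5557 = 0.836, so power is 79.8%.
- n = 60: (1.1619 − 1.1087)/0.5557 = 0.096, so power is 53.8%.

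Both stated figures reproduce (111 per arm is the strict minimum for 80%). The 53.8% identifies the method: at 60 per arm the unpooled formula gives 55.2%, the arcsine 55.1% and the continuity-corrected 44.6%. The 220 alone would not identify it, since at 110 per arm the unpooled and arcsine formulas give 80.8% and 80.7%.

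**2. Effect of the choice of test, with no assumption about AS.** Exact binomial enumeration at 110 per arm, 27.5% against 12.5%:

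| Test | Exact power |
|---|---|
| Pooled z, uncorrected | 80.4% |
| Fisher's exact | 75.8% |
| Continuity-corrected | 75.8% |

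The original 60 per group fits the corrected formula, in which |p1 − p2| is reduced by 1/n (80.3% at 60). The uncorrected formula needs only 53 per group and gives 85.2% at 60. So the two calculations in Section 14 do not follow the same formula, although the second is described as a repeat of the first.

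**3. Effect of adjusting for AS.** The documents give neither the AS distribution nor its association with admission, so both are assumed:

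- AS runs from 5 to 12, with 20%, 38% or 50% of patients severe (9 to 12).
- The odds ratio (OR) for admission per AS point is varied, with arm intercepts set so that the marginal rates stay at 27.5% and 12.5%.
- There are 20,000 simulated trials per setting at 110 per arm. The AS-adjusted likelihood-ratio test is compared with the unadjusted likelihood-ratio test on the same data.

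| OR per point | Odds ratio, AS 12 vs AS 5 (OR^7) | Gain in power (points) | Extra patients to which the gain in precision corresponds |
|---|---|---|---|
| 1.0 | 1 | −0.1 to 0.1 | about 0 |
| 1.2 | 3.6 | 0.8 to 1.2 | 4 to 5 |
| 1.35 | 8.2 | 2.4 to 2.5 | 12 to 16 |
| 1.5 | 17 | 4.2 to 4.8 | 25 to 31 |

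The last column is the variance ratio of the risk difference applied to 220; at OR 1.5, for example, 11.4% to 13.9% of 220 is 25 to 31. With equal arm rates of 20%, the type I error of the adjusted test was 5.0% to 5.3%. The 95% interval for the standardised risk difference covered 94.3% to 94.9% of the time at the planned rates.

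**4. Cross-check by formula.** If AS explains a share R² of within-arm outcome variance, the effective size is 110/(1 − R²) per arm. Putting that into the formula of step 1 gives 80.8% at R² = 0.025, 83.1% at 0.08 and 84.7% at 0.12: gains of 1.0, 3.2 and 4.8 points, the same range.

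**5. Sensitivity to the rates.** A 2:1 ratio at the observed 18.5% means 18.5 × 4/3 = 24.7% against 18.5 × 2/3 = 12.3%. The gains are then 1.0 to 1.1, 2.8 to 3.3 and 4.7 to 5.3 points at ORs of 1.2, 1.35 and 1.5.

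**The case against.** The strongest reply is that an unadjusted comparison of two proportions is a legitimate primary analysis, and that covariate adjustment is an optional refinement whose value rests on an association that the documents never state. This largely stands. All patients are already restricted to AS 5 to 12, and the top of the range needs a strong association. Part of the gain also depends on the likelihood-ratio test, since an adjusted Wald test has roughly 0.7 to 1 point less power. The case for adjusting is that it costs almost nothing, not that the plan fails without it.

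A reader might infer four stronger things that the documents do not support.

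- *That 220 is wrong.* It is not; step 1 reproduces it.
- *That leaving the test unnamed lowers power below 76%.* Omission changes nothing by itself. Only choosing Fisher's or a corrected test would, and no section proposes either. Nor is the planning method beyond inference: the current 53.8% points to the pooled uncorrected test, and only the superseded calculation points to a correction.
- *That a moderate association would bring 5 points.* That gain needs 17-fold odds across the eligible range.
- *That outcomes by arm have already been seen.* Section 3 says investigators are blinded to the assigned nebulizer, the interim look is described as blinded, and the weekly review in Section 11 is for safety and is not said to be by arm. Yet the principal investigator holds the envelopes (Section 4) and the case report forms record the nebulizer (Section 8). A dated confirmation is therefore reasonable; an accusation is not.

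**Conclusion.** The point holds as a low-cost improvement to a valid design. Section 14 describes no analysis that uses the eligibility AS. Adding it would be worth about 0 points of power if AS is not prognostic, about 1 at OR 1.2 per point, about 2.5 at 1.35, and about 5 only at 1.5. These figures rest on the assumed AS distribution and association, a log-linear effect of AS, and all 220 patients being analysed. Section 4 says of patients judged to be in impending respiratory failure that "they will be removed from the study and be treated according to physician orders"; selective loss of the sickest patients was not modelled and could weaken the AS association.

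The gap between 80.4% and 75.8% needs no such assumptions, but it arises only if one of the conservative tests is chosen. It is a further reason to name the test.

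**What to change.** Before outcomes by arm are seen, and with a dated statement confirming that they have not been, add a paragraph to Section 14 that specifies:

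- **Primary analysis:** logistic regression of admission on assigned nebulizer, with the eligibility AS as a continuous covariate.
- **Test:** the likelihood-ratio test for nebulizer at two-sided 0.05.
- **Estimate:** the standardised (marginal) risk difference with 95% CI.
- **Alongside:** the unadjusted comparison, without continuity correction.
- **Which score:** the initial AS that established eligibility. Section 4 says of the two study personnel, "One will administer all treatments with assigned nebulizer, perform pre-study assessments and note the start time of the treatment"; a score given after allocation by that person should not be the covariate.

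The cost is one paragraph, one extra model and the dated statement. No new data or patients are needed, because the score exists for everyone, including the 108 already counted. The change supplements the increase to 220 and does not replace it.
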